9.1.2 Serious Adverse Event (SAE)

A serious adverse event (SAE) is an AE occurring at any dose that results in any of the following outcomes:

- Death
- A life-threatening AE
- Inpatient hospitalization or prolongation of existing hospitalization
- A persistent or significant disability/incapacity
- A congenital anomaly/birth defect
- Results in a medically important event of reaction

Life-threatening in this context refers to a reaction in which the patient was at risk of death at the time of the reaction; it does not refer to a reaction that hypothetically might have caused death if more severe.

Medical and scientific judgment should be exercised in deciding whether other situations should be considered serious reactions, such as important medical events that might not be immediately life threatening or result in death or hospitalization, but might jeopardize the patient or might require

intervention to prevent one of the other outcomes listed above. Examples of such events are intensive treatment in an emergency room or at home for allergic bronchospasm, blood dyscrasias, or convulsions that do not result in hospitalization or development of dependency or abuse. Any suspected transmission via a medicinal product of an infectious agent is also considered a serious adverse reaction.

9.1.3 Suspected Adverse Reaction

Suspected adverse reaction means any AE for which there is a reasonable possibility that the study drug caused the AE. For the purposes of investigational new drug (IND) safety reporting, ‘reasonable possibility’ means there is evidence to suggest a causal relationship between the study drug and the AE.

9.1.4 Unexpected Adverse Event

An event is ‘unexpected’ if its specificity or severity is not consistent with the current clinical Investigator Brochure. It could include an event that may be symptomatically and pathophysiologically related to an event listed in the labeling, but differs from the event because of greater severity or specificity. Reports of death resulting from an AE are considered ‘unexpected’ unless the possibility of a fatal outcome from that AE is stated in the labeling.

9.1.5 Disease Related Events

PPHN is often associated with signs and symptoms of perinatal distress, including but not limited to, those listed in [Table 9-1](#). These events are anticipated to occur in the study population at some frequency independent of drug exposure. These events should be clearly documented in the subject medical record and identified as signs/symptoms of underlying disease under study.

Events that occur during the course of the study that are listed in Table 9-1 and felt to be related to the underlying disease under study by the Investigator will be recorded in the eCRF as disease related events. Events that are either serious or considered unusual with respect to intensity, frequency, or duration, or there is a reasonable possibility that it may have been caused by study drug as determined by the Investigator will also be recorded as an AE. All deaths, regardless of underlying cause, will be reported as an SAE.

Table 9-1 Expected Events Attributable to PPHN (System Organ Class and PREFERRED TERM, Ver. 17.0)

Hypoxia (Respiratory, thoracic & mediastinal disorders; HYPOXIA)	Pallor (Vascular disorders; PALLOR)
Cold extremities (General disorders and administration site conditions; PERIPHERAL COLDNESS)	Cyanosis (Cardiac disorders; CYANOSIS)
Cardiac arrhythmia (Cardiac disorders; ARRHYTHMIA)	Coagulopathy (Blood and lymphatic system disorders, COAGULOPATHY)
Tachypnea (Respiratory, thoracic & mediastinal disorders; TACHYPNOEA)	Respiratory distress (Respiratory, thoracic and mediastinal disorders; RESPIRATORY DISTRESS)
Polycythemia (Blood and lymphatic system disorders, POLYCYTHAEMIA)	Hyperviscosity syndrome (Blood and lymphatic system disorders, HYPERVISCOSITY SYNDROME)
Cardiovascular collapse (Vascular disorders; CIRCULATORY COLLAPSE)	Asphyxia (Respiratory, thoracic and mediastinal disorders; ASPHYXIA)
Postoperative hypotension (Vascular disorders, PROCEDURAL HYPOTENSION)	Tachycardia (Cardiac disorders; TACHYCARDIA)
Cor pulmonale (Cardiac disorders; COR PULMONALE)	Urine output decreased (Investigations, URINE OUTPUT DECREASED)
Weight loss (Investigations; WEIGHT DECREASED)	Shock (Vascular disorders; SHOCK)
Edema (General disorders and administration site conditions; OEDEMA)	Hepatomegaly (Hepatobiliary disorders; HEPATOMEGALY)
Respiratory failure (Respiratory, thoracic and mediastinal disorders; RESPIRATORY FAILURE)	

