1.2 REMODULIN (TREPROSTINIL) BACKGROUND

Treprostinil is a chemically stable tricyclic analogue of prostacyclin (PGI₂), which is approved for the treatment of pulmonary arterial hypertension (PAH) in the US, EU, and many other countries under the brand name Remodulin. The pharmacology of treprostinil has been extensively characterized for the treatment of PAH using either a subcutaneous (SC) or intravenous (IV) continuous infusion. A detailed description of preclinical and clinical information of treprostinil for injection is provided in the Investigator's Brochure.

The major pharmacological actions of treprostinil are direct vasodilatation of pulmonary and systemic arterial vascular beds and inhibition of platelet aggregation. *In vitro*, treprostinil induced concentration dependent relaxation of rabbit isolated precontracted mesenteric arteries, inhibition of adenosine diphosphate (ADP), induced aggregation in human platelet rich plasma, and inhibition of ADP induced platelet aggregation in rat platelet rich plasma. In animals, the vasodilatory effects of treprostinil reduce right and left ventricular afterload, increasing cardiac output and stroke volume. Prostacyclins lower pulmonary artery pressure, increase cardiac output without affecting the heart rate, improve systemic oxygen transport as well as possibly reversing pulmonary arterial remodeling. There is also increasing evidence that the ability to block the proliferation of pulmonary artery smooth muscle cells may contribute, along with the capacity to produce vasodilatation and inhibition of platelet aggregation, to the therapeutic effects of prostacyclins in the treatment of PAH. The mechanism of action is therefore likely to be multifactorial.

The efficacy of Remodulin in adult patients with PAH has been established in both the IV and SC routes (5-7). However, there is a growing body of literature to support the use of Remodulin in the pediatric population. Multiple published reports of the use of chronic Remodulin in children as young as 20 weeks of age have been reported without unexpected adverse events (AEs) (8-10). Acute dosing of SC and IV Remodulin has been used in children as young as 6-8 weeks, including a case report published regarding the use of IV

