12.4.3 PPHN Disease-related Events

The number and percentage of subjects who experienced any PPHN disease-related event will be summarized by treatment group. Each category of disease-related event will also be summarized by treatment group. A listing of PPHN disease-related events will also be provided.

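### No planned table gives the total per-arm incidence of Table 9-1 events such as shock or circulatory collapse, because adverse events and disease-related events are tabulated separately and can overlap

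*Protocol*

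**What the plan says.** - **Routing.** Protocol 9.1.5 sets a recording rule for the terms of Table 9-1: those "felt to be related to the underlying disease under study by the Investigator will be recorded in the eCRF as disease related events". The rule applies only to listed terms.
- **Dual recording.** The same section adds a second entry in three situations. "Events that are either serious or considered unusual with respect to intensity, frequency, or duration" form the first two. A reasonable possibility that study drug caused the event is the third. Such events, "as determined by the Investigator will also be recorded as an AE". All deaths are reported as SAEs.
- **The list.** Table 9-1 contains "Shock (Vascular disorders; SHOCK"), circulatory collapse and coagulopathy. For low blood pressure it contains only "Postoperative hypotension (Vascular disorders, PROCEDURAL HYPOTENSION").
- **The drug.** Protocol 1.2 gives the major actions of treprostinil as "direct vasodilatation of pulmonary and systemic arterial vascular beds and inhibition of platelet aggregation". Protocol 4.3.1 names hypotension and bleeding as risks with certain co-medications.
- **The AE analysis.** SAP 12.2 summarises treatment-emergent AEs by system organ class and preferred term (Tables 14.3.1.x), coded to the latest MedDRA version.
- **The disease-related event analysis.** SAP 12.4.3 says: "The number and percentage of subjects who experienced any PPHN disease-related event will be summarized by treatment group." Each category is summarised by arm as well (Table 14.3.3). The section gives no coding version and no treatment-emergence rule. Table 9-1 cites MedDRA version 17.0.
- **Combined output.** The list of tables in SAP 15.1 has none that joins the two records.

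**The concern.** Shock, circulatory collapse and procedural hypotension can come from PPHN or from a systemic vasodilator. In one infant the two causes are hard to separate. A randomised trial can separate them at group level by comparing how often the event occurs in each arm, whatever anyone believes caused it. The plan never displays that comparison. An ordinary, non-serious listed event that the investigator attributes to PPHN, and not possibly to study drug, stays out of the AE tables.

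Safety is part of the primary objective (Protocol 2.1). Its analysis is descriptive, with a focus on incidence and no inferential tests (Protocol 10.3.3). The tables are therefore the safety analysis, and a quantity that no table shows is one that the report's readers will not see.

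**Working it through.** The plan states no figure on this point, so there is none to reproduce. The check traces the recording rule to the outputs and then asks what a reader could recover from the two planned tables.

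**Step 1. Where can one listed event end up?**

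| Table 9-1 event judged due to PPHN | Disease-related event record | AE record |
|---|---|---|
| Not serious, not unusual, not possibly drug-caused | Yes | No |
| Serious, unusual, or possibly drug-caused | Yes | Yes |

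A listed event that is not attributed to PPHN goes to the AE record only. An infant with two episodes of one term can therefore appear in either table or in both.

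**Step 2. What do the two tables determine?** For one term in one arm of n infants, let a be the number in the AE table and b the number in the disease-related event table. The number with the event from either source is a + b minus the number in both. The overlap is not tabulated, so the total lies between max(a, b) and min(n, a + b).

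**Step 3. Size, with assumed counts.** n = 33 is the planned arm size (Protocol 10.2). The counts are assumptions, because the documents give no event rates.

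| a | b | Lowest total | Highest total |
|---|---|---|---|
| 3 | 3 | 3/33 = 9.1% | 6/33 = 18.2% |
| 6 | 6 | 6/33 = 18.2% | 12/33 = 36.4% |
| 4 | 8 | 8/33 = 24.2% | 12/33 = 36.4% |

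**Step 4. What this does to a comparison of arms.** Suppose treprostinil shows 6 and 6, and placebo 3 and 3.
- Complete overlap in both arms: 6 v 3, a difference of 3/33 = 9.1 points.
- No overlap in either arm: 12 v 6, a difference of 6/33 = 18.2 points.
- Outer limits, if overlap differs fully by arm: 6 v 6 (0 points) to 12 v 3 (9/33 = 27.3 points).

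**Step 5. Is there a fixed dilution of the AE table?** Assume 40% v 15% of infants have the event from any source, with one event each, and that a share s in both arms is recorded as disease-related only. The AE table then shows a difference of 25 × (1 − s) points: 18.75 for s = 25%, 12.5 for s = 50% and 6.25 for s = 75%. The documents give no value for s, so no single dilution factor can be claimed. The remaining difference appears by arm in Table 14.3.3.

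**Step 6. Could a reader join the two tables by hand?** Not reliably. AE summaries are limited to treatment-emergent events, and SAP 12.4.3 states no such limit. The MedDRA version is stated differently in the two places. The overlap has to be found from Listings 16.2.7.2 and 16.2.8.5.

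**The case against.** The plan contains no contradiction here and loses no data. Each table shows its own part by arm. Both records are listed. Blood pressure and heart rate (SAP 12.4.2), and platelet count and prothrombin time with shift tables (SAP 12.3.2), are summarised by arm free of any attribution. Serious, unusual and possibly drug-caused events reach the AE tables in any case. Shock or collapse in a ventilated neonate will often be serious, so the set recorded only as disease-related may be small for those terms. Extra analyses are also allowed for.

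Most of this stands, and it sets the weight of the point. Two parts do not remove it. The safeguards for unusual and possibly drug-caused events rest on the investigator's judgement, which is the same attribution that the comparison should not depend on. Vital signs summarised at scheduled times do not count infants who had an episode.

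A reader might infer several stronger things that the documents do not support:
- **That hypotension is diverted from the AE tables.** Only the postoperative or procedural term is listed. General hypotension, which the protocol gives as its example of a dose-limiting event, is not.
- **That tachycardia is a drug-matching term.** It is listed ("Tachycardia (Cardiac disorders; TACHYCARDIA"), but Protocol 1.2 describes the class as leaving heart rate unchanged. Coagulopathy fits only loosely, since the stated action is on platelets.
- **That the split halves the counts.** That assumes a 50% share and no dual recording, and the protocol provides for dual recording.
- **That suspected active treatment steers events out of the AE tables.** No passage shows this. An investigator who suspected the drug would be adding an AE entry under the rule.

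**Conclusion.** The point holds as a modest gap in the planned display. For a Table 9-1 term, the per-arm incidence regardless of attribution is known from the planned tables only between max(a, b) and min(n, a + b). With assumed counts of 6 and 6 of 33, that is 18.2% to 36.4%. The actual width depends on event rates and on the overlap between the two records, and the documents give neither. It will be narrow for terms that are nearly always serious. The interest is greatest for shock, circulatory collapse and procedural hypotension, where the protocol's own account of systemic vasodilatation overlaps with the disease. Nothing here shows that harm would be hidden or that the safety conclusions would be wrong. It is an inexpensive improvement, not a defect that threatens the trial.

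**What to change.** Add one table to SAP 12.2 and to the list in SAP 15.1, on the Safety population by treatment received:
- Rows: the Table 9-1 terms, plus hypotension and bleeding terms, so that procedural hypotension is read beside hypotension recorded as an AE.
- Source: the AE record or the disease-related event record, coded to the same MedDRA version.
- Timing: the treatment-emergence rule that SAP 12.2 already sets for AEs, applied to both sources.
- Counting: each infant once per term.
- Alongside: the number with an AE entry and the number with a disease-related entry only.

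Keep the existing tables as support. Specify the table before unblinding, so that it is planned rather than post hoc.

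The cost is one extra table and a coding and date alignment step for the disease-related events. No new data collection is needed, and no recording or clinical rule changes.

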9.2 DOCUMENTATION OF ADVERSE EVENTS

An AE or SAE occurring during the study must be documented in the subject's source documents and on the appropriate eCRF page. Information relating to the AE such as onset and cessation date and time, intensity, seriousness, relationship to study drug, and outcome is also to be documented in the eCRF (see Appendix 15.1 for definitions). Serious AEs are to be reported on the SAE Notification Form and submitted within 24 hours to United Therapeutics Global Drug Safety (Section 9.4). Where possible, AEs/SAEs should be recorded using standard medical terminology. If several signs or symptoms are clearly related to a medically-defined diagnosis or syndrome, the diagnosis or syndrome should be recorded on the eCRF page, not the individual signs and symptoms (e.g., pneumonia characterized by shortness of breath and wheezing).

9.3 PERIOD OF OBSERVATION

For the purposes of this study, the period of observation starts from the time the informed consent is signed and concludes upon meeting screen failure criteria, at the time of death, at the time of hospital discharge, at the time of withdrawal from the study, or at 4 weeks after last dose of study drug, whichever comes first. Day 28 will be considered as the last day of study drug administration for subjects who continue on Remodulin. Subjects with ongoing AEs at the time of hospital discharge will continue to be followed for their AEs until either resolution (or return to normal or Baseline values), until judged by the Investigator to no longer be clinically significant, or until 4 weeks after last dose of study drug. All SAEs should be followed until resolution, death, or the subject is lost to follow-up, even if they are ongoing more than 4 weeks after the last dose of study drug.

If the subject receives commercial Remodulin after hospital discharge, beyond Day 56/End of study, or following withdrawal from the study, AEs/SAEs will be subject to AE/SAE reporting under local government post-marketing AE/SAE reporting requirements.

Supplemental measurements and/or evaluations may be necessary to investigate fully the nature and/or causality of an AE or SAE. This may include additional laboratory tests, diagnostic procedures, or consultation with other healthcare professionals. The eCRF pages should be updated with any new or additional information as appropriate.

If the Investigator detects an SAE in the study subject after the end of the period of observation, and considers the event possibly related to prior study treatment, he or she should contact the Sponsor to determine how the event should be documented and reported.

9.4 REPORTING RESPONSIBILITIES OF THE INVESTIGATOR

All SAEs, regardless of expectedness or causality, must be reported to the Sponsor by fax [REDACTED]
[REDACTED] or email [REDACTED] within 24 hours of awareness.

A completed SAE Notification Form along with any relevant hospital records (e.g., discharge summary), death certificates and autopsy reports (if performed) should be faxed to United Therapeutics Global Drug Safety Department. A follow-up SAE Notification Form must be forwarded to the United Therapeutics Global Drug Safety Department within 24 hours of the receipt

of any new/updated information or medical records. The Investigator must also promptly notify their Investigational Review Board (IRB) or Ethics Committee (EC) of the SAE, including any follow-up information, in accordance with applicable national regulations and guidelines set forth by the IRB or EC.

9.5 SAFETY REPORTS

In accordance with FDA, European, and national regulations, the Sponsor will notify the FDA, other competent authorities, and all participating Investigators of any AE that is considered to be possibly attributable to study drug and is both serious and unexpected. The Investigator must report these AEs to their IRB or EC in accordance with applicable national regulations and guidelines set forth by the IRB or EC.

10 STATISTICAL CONSIDERATIONS

10.1 DATA PROCESSING

Data collection will begin during screening (i.e., once the informed consent form has been signed). Subjects will be assigned a separate screening number until they are randomized, after which a separate subject number will be assigned for subjects enrolled into the study.

Subject data will first be documented in the subject's source documents, and then transferred into the eCRF. All data entered into the eCRF should have a corresponding source document. Site personnel will be responsible for recording all subject data into the eCRF. The eCRF pages are to be reviewed by the Principal Investigator for completeness and accuracy. The Principal Investigator must sign each subject's eCRF to signify their approval of the data. The database will be considered final when all outstanding queries have been resolved and all data management quality control procedures are complete.

10.2 SAMPLE SIZE

Based on the systematic review of use of nitric oxide for respiratory failure in infants by Finer and Barrington, 57.9% (194/335) subjects in control group had an outcome of death or requirement for EMCO (18). In this study, assuming 60% subjects in placebo group and 30% subjects in Remodulin group with an outcome of death, requirement for EMCO, or need for additional PAH therapy, we calculated that 66 subjects (33 subjects per treatment group) will have at least 80%

power to show a significant difference in favor of Remodulin at alpha level of 0.05 (one-sided test). Approximately 70 subjects are planned to be randomized (1:1) to either receive treatment with Remodulin or placebo on top of the standard of care.

10.3 ANALYSIS PLAN

10.3.1 Primary Endpoint

Efficacy analyses will be performed in intention to treatment (ITT) population where ITT population includes all randomized subjects who have successfully initiated the study treatment.

The primary endpoint is clinical worsening (need for additional treatment [initiation of another targeted pulmonary vasodilator therapy], initiation of ECMO or death) between Baseline and Day 14 or time of discharge from the hospital, whichever comes first. It will be analyzed as a binary endpoint using the percentage of subjects who meet the definition of clinical worsening within each treatment group. Subjects who meet the definition of clinical worsening after Day 14 will not be counted towards the primary endpoint. Chi-square test will be used to test for the treatment difference.

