3.3 CLINICAL ASSESSMENTS

3.3.1 *Efficacy*

3.3.1.1 *Assessment of Clinical Worsening*

Efficacy will be assessed by a composite primary endpoint of clinical worsening assessed at Day 14 or hospital discharge, whichever comes first, as defined by one of the following events:

- Death
- Initiation of ECMO per institutional policies
- Need for additional treatment (initiation of additional targeted pulmonary vasodilator therapy for PPHN)

Clinical worsening will be evaluated from Baseline (initiation of study drug) to the time of discontinuation of study drug, discharge from the hospital, or at the conclusion of Day 14, whichever comes first. Events occurring after the first 14 days of treatment will not count towards the primary endpoint.

3.3.1.1.1 *Need for Additional Treatment*

The following criteria should be met prior to initiation of additional targeted pulmonary vasodilator therapy for PPHN (all criteria required):

- OI measurement >20
- In the clinical judgment of the Investigator, subject requires addition of another targeted pulmonary vasodilator therapy (e.g., PDE-5i, ERA, alternate prostanoid [epoprostenol, iloprost], L-citrulline) due to worsening of clinical status or unsatisfactory clinical response
- Subject has received study drug for at least 24 hours and reached a minimum dose of 10ng/kg/min, or is unable to tolerate further increases (e.g., due to systemic hypotension); **OR**
 - If less than 24 hours, subject has two consecutive OI measurements >30 separated by at least one hour **OR** two consecutive arterial lactate levels of $\geq 4\text{mmol/L}$ separated by at least one hour

If an additional pulmonary vasodilator therapy is added after Day 14, the subject will not meet the primary endpoint definition of clinical worsening.

3.3.1.1.2 *Extracorporeal Mechanical Oxygenation (ECMO)*

ECMO will be initiated per institutional policy. Any subject who initiates on ECMO during the first 14 days of the study will meet the definition of clinical worsening. The initiation of ECMO after Day 14 will not be considered a clinical worsening event for the purposes of the primary endpoint of the study.

3.3.1.1.3 *Death*

Any subject who dies within the first 14 days of the study will meet the definition of clinical worsening. Deaths that occur after Day 14 will not be considered a clinical worsening event for the purposes of the primary endpoint of the study.

All deaths will be reported as a serious adverse event (SAE) (Section 9).

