3.4 NUMBER OF CENTERS

Approximately 40 centers are planned.

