4.2 EXCLUSION CRITERIA

A subject is ineligible for participation if any of the following criteria are met:

1. Previous or concurrent use of a PDE-5i, ERA or prostanoid. Previous receipt of prostaglandin E1 for ductal patency is allowed.
2. Significant congenital heart disease (CHD) as detected by ECHO (excluding presence of minor defects such as small secundum ASD, minor valvular abnormalities, or expected transitional findings such as a PFO, or PDA. Subjects with small muscular, restrictive VSD may be enrolled).
3. Clinically significant, untreated active pneumothorax at Screening.
4. Evidence of clinically significant bleeding (e.g., hemodynamic instability or requiring transfusion) at Screening. Note: history of a transfusion is not necessarily an exclusion criterion.
5. Necrotizing enterocolitis; defined as Bells stage II or greater at Screening.
6. Uncontrolled hypotension; defined as mean systemic pressures less than or equal to 35mmHg at Screening.

7. Uncontrolled coagulopathy and/or untreated thrombocytopenia; defined as <50,000 platelets / μ L at Screening.
8. History of severe (Grade 3 or 4) intracranial hemorrhage at Screening. Note: a cranial ultrasonography is not required during Screening.
9. Currently receiving ECMO or has immediate plans to initiate ECMO.
10. Expected duration on mechanical ventilation of less than 48 hours.
11. Life expectancy is less than two months or has a lethal chromosomal anomaly.
12. Contraindication to ECMO.
13. Bilateral congenital diaphragmatic hernia.
14. Active seizures at Screening.
15. Currently participating in another clinical drug study (excluding observational registries).

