2.1 PRIMARY ENDPOINT

The primary endpoint is the composite endpoint of clinical worsening through Day 14 as defined by one of the following:

- Death
- Initiation of extracorporeal mechanical oxygenation (ECMO) per institutional policies
- Need for additional treatment (initiation of an additional targeted pulmonary vasodilator therapy [eg, phosphodiesterase type 5 inhibitor {PDE-5I}, endothelin receptor antagonist {ERA}, prostanoid, L-citrulline}]

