8.5.3 Time to Event and Censor Status

Time to event and censor status will be calculated based on the rules in Table 8-1 for time to clinical worsening, time to initiation of ECMO, and time to discontinuation of iNO.

Table 8-1 Time to Event and Censor Status Rules

Parameter	Scenario	Formula	Censor Status
Time to Clinical Worsening (days)	Subject with clinical worsening or subject died between Baseline and Day 14	= minimum of (Worsening date, death date) - Randomization date	0 (event)
	Subject without clinical worsening between Baseline and Day 14	= minimum of (Last assessment date - Randomization date, 14)	1 (censored)
Time to initiation of ECMO (days)	Subject initiated ECMO between Baseline and Day 14	= Initiation date - Randomization date	0 (event)
	Subject did not initiate ECMO between Baseline and Day 14	= minimum of (Last assessment date - Randomization date, 14)	1 (censored)
Time to discontinuation of iNO (days)	Subject discontinued iNO between Baseline and Day 14	= iNO discontinuation date - Randomization date	0 (event)
	Subject did not discontinue iNO between Baseline and Day 14	= minimum of (Last assessment date - Randomization date, 14)	1 (censored)

ECMO, extracorporeal mechanical oxygenation; iNO, inhaled nitric oxide

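### The primary-endpoint window closes at hospital discharge in some sections and at Day 14 in others, so an infant transferred before Day 14 has no single defined outcome

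*Protocol*

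**What the plan says.** Sections that close the window at discharge:

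- Protocol 10.3.1 counts events "between Baseline and Day 14 or time of discharge from the hospital, whichever comes first". Footnote j of Table 3-1 and the opening sentence of 3.3.1.1 use the same limit.
- A later sentence in 3.3.1.1 evaluates worsening from Baseline "to the time of discontinuation of study drug, discharge from the hospital, or at the conclusion of Day 14, whichever comes first". This adds a third stopping point, the end of study drug, which 10.3.1 and footnote j do not have.

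Sections that run to Day 14 regardless of discharge:

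- Protocol 3.3.1.1.2: "Any subject who initiates on ECMO during the first 14 days of the study will meet the definition of clinical worsening". Section 3.3.1.1.3 says the same for death.
- SAP 2.1: "The primary endpoint is the composite endpoint of clinical worsening through Day 14". SAP 10.1.1.2 analyses it on that basis.
- SAP Table 8-1 has the event row "Subject initiated ECMO between Baseline and Day 14" and a matching row for worsening or death. Neither has a discharge limit.

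Two further rules affect the scoring. SAP 8.3.1 assigns Yes to any missing worsening status. SAP 10.2.5 takes worsening status from the clinical-worsening page of the eCRF.

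Discharge is not defined in either document, and transfer between hospitals is not mentioned. Protocol 3.1 ends post-treatment data collection at hospital discharge, except for follow-up of ongoing AEs and of SAEs.

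**The concern.** ECMO is a component of the primary endpoint. Protocol 1.1 describes it as the usual course for critically ill neonates who do not respond to iNO, and criterion 12 of section 4.2, "Contraindication to ECMO", leaves only infants who could receive it. Section 3.4 states "Approximately 40 centers are planned", and nothing in the protocol requires a site to provide ECMO. If an infant has to leave the study hospital to receive it, the event falls after what some sections treat as the end of the window.

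Infants transferred for that reason would be treatment failures, so any error in scoring them is related to outcome. The time-to-event analyses are exposed too. Table 8-1 censors an infant without a recorded event at the last assessment, which here could fall just before the event. Analysis cannot recover events that were never collected.

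**Working it through.** **Step 1. One infant under each rule.** Take an infant transferred on Day 3 who starts ECMO at the receiving hospital on Day 4.

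| Rule applied | Condition | Score |
|---|---|---|
| Protocol 10.3.1, footnote j | Transfer treated as discharge; window closed on Day 3 | Not worsened |
| Protocol 3.3.1.1.2, SAP 2.1, Table 8-1 | The ECMO start is known | Worsened |
| SAP 8.3.1 | Worsening status recorded as missing | Worsened, by imputation |

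If a transferred infant had no event but was recorded as missing, the third rule would give a false Yes. Error is therefore possible in both directions.

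The first row is a practical possibility. Protocol 7.3.2.1 asks for the Day 14 assessments, including clinical worsening, before an early discharge. A site that treats transfer as discharge could complete the page as no event on Day 3. The status would then not be missing, and SAP 8.3.1 would not apply.

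**Step 2. The plan's sample size.** Inputs from Protocol 10.2: 60% v 30%, one-sided alpha 0.05, 80% power. The mean proportion is 0.45.

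n = [1.645 × √(2 × 0.45 × 0.55) + 0.842 × √(0.60 × 0.40 + 0.30 × 0.70)]² / 0.30² = 32.9, rounded up to 33 per arm.

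This reproduces the stated 66. Power at 33 per arm is 80.1% one-sided. It is 69.6% at the two-sided 0.05 level of SAP section 8.

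**Step 3. Sensitivity of the primary test.** With 33 per arm and x v y events (placebo v Remodulin), the uncorrected Pearson statistic reduces to

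χ² = 66(x − y)² / [(x + y)(66 − x − y)].

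| Placebo v Remodulin | χ² | Two-sided p |
|---|---|---|
| 19 v 11 | 66 × 64 / (30 × 36) = 3.91 | 0.048 |
| 18 v 11 | 66 × 49 / (29 × 37) = 3.01 | 0.083 |
| 20 v 10 | 66 × 100 / (30 × 36) = 6.11 | 0.013 |
| 19 v 10 | 66 × 81 / (29 × 37) = 4.98 | 0.026 |
| 18 v 10 | 66 × 64 / (28 × 38) = 3.97 | 0.046 |
| 17 v 10 | 66 × 49 / (27 × 39) = 3.07 | 0.080 |

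From 19 v 11, one lost placebo event crosses 0.05. From 20 v 10, which is close to the planned rates, three are needed. Each event is 1/33 = 3.0 percentage points of an arm.

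**Step 4. Power if events are lost in both arms.** The documents give no transfer rate, so the loss fractions are assumptions.

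| Share of events scored as not worsened | Rates | Expected events lost (placebo, Remodulin) | Power one-sided | Power two-sided |
|---|---|---|---|---|
| 0% | 60% v 30% | 0, 0 | 80.1% | 69.6% |
| 5% | 57% v 28.5% | 1.0, 0.5 | 76.6% | 65.4% |
| 10% | 54% v 27% | 2.0, 1.0 | 73.0% | 61.2% |
| 20% | 48% v 24% | 4.0, 2.0 | 65.5% | 52.9% |

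**The case against.** A reader might infer that an infant moved elsewhere for ECMO is scored as not worsened. The documents do not say so. That score requires transfer of a ventilated infant to count as discharge, and it requires 10.3.1 to override 3.3.1.1.2 and the SAP. If the status is left missing, SAP 8.3.1 gives the opposite score. This objection stands: the finding is an unresolved conflict, with no established direction.

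A reader might also infer that all data collection stops at discharge. It does not. Protocol 3.1, 3.3.2.4 and 9.3 continue follow-up of ongoing AEs and of SAEs. Section 9.1.5 makes every death an SAE, and 9.4 asks for relevant hospital records and death certificates. A failing infant could well leave with an open SAE, so some outcomes would reach the sponsor. That stands too, with a limit. For an SAE detected after the observation period, 9.3 asks the investigator to contact the sponsor only if it is considered possibly related to study treatment. No rule carries SAE information to the worsening page from which the endpoint is taken.

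No document shows that any site lacks ECMO. Protocol 6.1.5 allows study drug to continue during ECMO and leaves later weaning to the investigator, which fits ECMO at the study hospital. The number of affected infants could be zero.

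Finally, the p-value examples put every loss on placebo and use the SAP's two-sided test. At the one-sided 0.05 level used for sizing, 18 v 11 has p = 0.083 / 2 = 0.041 and 17 v 10 has p = 0.080 / 2 = 0.040, both still significant. It would be wrong to say that one or two transfers in general change the conclusion.

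**Conclusion.** The window is defined inconsistently within the protocol and between protocol and SAP. Transfer is not addressed, and endpoint ascertainment after the infant leaves is not specified. A transferred infant's primary outcome therefore depends on which section is applied and how the eCRF page is completed.

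The size is conditional. Roughly one to three misclassified events in one arm could move a two-sided p across 0.05. This assumes 33 per arm, the uncorrected chi-square test, losses confined to one arm, and starting tables between 19 v 11 and 20 v 10. How many infants would be transferred, and in which direction the error would run, cannot be determined from the documents.

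Severity is moderate. This is a Phase II trial with an exploratory objective and an unknown, possibly zero, number of cases. The correction is nevertheless cheap and has to be made while outcomes can still be collected.

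**What to change.** 1. Align Protocol 3.3.1.1, 10.3.1 and footnote j with 3.3.1.1.2, 3.3.1.1.3 and the SAP, so that one window running through Day 14 applies throughout. Resolve the extra stop at study-drug discontinuation in 3.3.1.1 in the same edit.
2. State that transfer to another hospital does not end the window.
3. For each transferred infant, obtain from the receiving hospital vital status, ECMO start and targeted pulmonary vasodilator start, with dates and times, through Day 14. Enter them on the clinical-worsening eCRF page.
4. Record transfer as its own disposition, separate from discharge.

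The cost is a short protocol edit, a consent line permitting contact with the receiving hospital, one eCRF code and one contact per transferred infant. The planned sample size and clinical care do not change.
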